A Novel Negative Pressure Isolation Device Reduces Aerosol Exposure: A Randomized Controlled Trial

Study Protocol and Statistical Analysis Plan

Trial Registration: ClinicalTrials.gov, NCT 04864236

June 28, 2021

Principal Investigator:

[name]

[contact]

UCLA Department of Anesthesiology and Perioperative Medicine, [name]

Inclusion criteria:

Adult patients (age>18) undergoing elective surgery requiring general endotracheal anesthesia

Exclusion criteria:

Patients with BMI > 40 kg/m², or

Patients predicted to be difficult mask ventilation or intubation (as determined by anesthesiologist), or

Patients refusing to consent for any reason (ie. claustrophobia or inability to cooperate).

Preoperative:

Patients will be screened and identified by the study team and allocated to each group via simple randomization (1:1), which will occur as soon as the OR schedule is available for viewing.

Patients will be randomized to either device or no device. The study investigator will obtain consent the day of surgery. Also at the time of randomization, the anesthesia providers involved will be informed and asked to review the study protocol. Only the study investigators will be involved in the use of the device during patient care.

On the day of surgery, the primary anesthesia provider will be provided with the unassembled device (if assigned to the device group) and be asked to assemble it. This process will be observed and timed by a study coordinator.

Intubation:

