For device group: one of the study investigators will place the device around the patient's head. At this time, one particle counter will be positioned on an IV pole next to the study investigator at the level of his/her nose. A second particle counter will be positioned next to the patient's head in order to take measurements from inside of the device. The study team will obtain baseline measurements from both inside and outside the device simultaneously. At the start of preoxygenation (routine part of anesthesia), the study team will begin nebulizing 5ml of saline using a standard nebulizer at 5 liters per minute of oxygen flow. A study team member will be holding the nebulizer close to the patient's nose and mouth. This will simulate airborne contamination that is generated by the patient. During this process, the patient will be instructed to breathe normally for 1 minute, then breathe deeply for 1 minute, and then breathe normally again for 1 minute. During intubation (routine part of anesthesia), the nebulizer will be placed next to the patient's head and it will be kept on until after the patient has been intubated.

Concurrent with the start of preoxygenation, the particle counter will start measuring particle counts. 1 minute after the endotracheal tube or laryngeal mask airway is secured, the anesthesia provider will be instructed to remove the device. A study coordinator will record particle counts continuously until 2 minutes after the device is removed from around the patient's head.

For no device group: exactly the same except no device will be placed around patient's head.

Digital recordings of the particle counts and distribution of particle sizes will be recorded during the conduct of the study in the operating room. These recordings will not be stored with any personally identifiable information. These recordings will be stored on a secure laptop

(university-owned and encrypted) that is accessible only to the study investigators. If the participant decides to withdraw from the study, the study investigators will destroy the recordings immediately.

Statistical Methods:

Primary outcome: particle count measurements during intubation

Statistical analysis plan:

Particle counts will be compared between groups (device vs no device) using an independent samples t-test (or Wilcoxon Rank Sum Test if distributional assumptions are violated).

Power/sample size:

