- 1) From a statistical perspective, a sample size of 10 per group allows us to detect an effect size as small as 1.35 between groups (using a t-test, >80% power, two sided alpha 0.05). A similar study (17) exploring the effectiveness of several different containment devices on airborne particles in similar settings mentioned an effect size of 1.0 (20,000 particles vs 12,000, SD of 8,000). We hypothesize that our device will be more effective than any device tested in this previous study at reducing airborne contamination so this is a conservative estimate of what we expect to see with our device.
- 2) Ultimately, we envision a final sample size of 50 per group to better assess both efficacy of the primary outcome as well as increase reliability in our secondary outcomes. This sample size will allow us to detect effect sizes as low as 0.57 between groups (using a t-test, >80% power, two sided alpha 0.05) and gives us a measure of precision of a confidence interval for the mean on our primary outcome of within +/-2,273 particles assuming the box group is 12,000 with a SD of 8,000.(17)

Secondary outcomes:

time to intubation (defined as time from the first entry of laryngoscope into pt's oropharynx to the time of confirmed successful tracheal intubation),
total number of intubation attempts,
pre-op airway assessment (Mallampati score and thyromental distance),
laryngoscopy grade view (Cormack-Lehane) obtained during intubation

Analysis plan:

Secondary outcomes will be compared between groups (where possible) using an independent samples t-test (or chi-square test) as appropriate.

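### The primary test is chosen from the observed data by an unstated rule, the Wilcoxon branch has no planned effect estimate, and the collected baseline counts go unused

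*Combined protocol and SAP*

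**What the plan says.** All references are to the combined protocol and SAP.

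- **Statistical Methods.** The endpoint is given as "Primary outcome: particle count measurements during intubation". The groups are compared by an independent samples t-test, "or Wilcoxon Rank Sum Test if distributional assumptions are violated". No assumption, diagnostic, threshold or decision-maker is named, and no estimate or interval is attached to the Wilcoxon result.
- **Power/sample size, item 1.** The plan states that "a sample size of 10 per group allows us to detect an effect size as small as 1.35 between groups", for a t-test. It cites an earlier study with 20,000 against 12,000 particles and an SD of 8,000, and expects its own device to do better.
- **Power/sample size, item 2.** It adds that "we envision a final sample size of 50 per group", with a detectable effect size of 0.57, again for a t-test. It gives a half-width of 2,273 particles for a mean, "assuming the box group is 12,000 with a SD of 8,000".
- **Intubation, device group.** Once the device and counters are in place, "The study team will obtain baseline measurements from both inside and outside the device simultaneously". The analysis plan does not mention these readings again.

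**The concern.** A t-test addresses a difference in mean counts. A Wilcoxon test addresses whether counts in one arm tend to exceed those in the other. If the observed data decide between them by an unwritten criterion, the trial's question is not fixed in advance, and two analysts could defensibly report different primary results. If the rank test is used, the plan as written yields a p-value with no stated size of the reduction in exposure, which is what the trial sets out to measure.

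The planning figures make the fallback a live prospect, because the outcome cannot be negative and the assumed SD is two thirds of the assumed device-arm mean.

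The comparison also leaves out the baseline counts, which the team already collects and which could sharpen the estimate at no extra measurement cost.

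**Working it through.** **Inputs from the plan.** Means 20,000 and 12,000; SD 8,000; 10 or 50 per group; two-sided alpha 0.05; detectable effects 1.35 and 0.57; half-width 2,273.

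**1. The plan's own figures reproduce.**
- Noncentral-t power at 50 per group and d = 0.57 is 80.6%. The smallest effect detectable with 80% power is 0.566.
- At 10 per group and d = 1.35, power is 81.4%. The smallest detectable effect is 1.325.
- Half-width for one group's mean: t(0.975, 49 df) × 8,000/√50 = 2,273.6.

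**2. Exact normality is impossible in the device arm.** Φ((0 − 12,000)/8,000) = Φ(−1.5) = 0.0668. That is 50 × 0.0668 ≈ 3.3 patients in 50 with negative counts. For the 20,000 arm, Φ(−2.5) = 0.006.

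**3. Chance of a switch, and power of each test, at 50 per group.** The plan gives neither a distribution nor a check, so both are assumed here: five shapes matched to the plan's means and SD, and Shapiro-Wilk at 5%, applied either to each arm (switch if either fails) or to the pooled residuals. There were 3,000 simulated trials per setting. Switch columns use 20,000 against 12,000. Power columns use d = 0.57, that is 12,000 + 0.57 × 8,000 = 16,560 against 12,000.

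| Assumed shape | Switch, either arm | Switch, pooled residuals | t-test power | Wilcoxon power |
|---|---|---|---|---|
| Normal (reference only) | 10% | 5% | 80% | 78% |
| Zero-truncated normal | 71% | 38% | 80% | 83% |
| Weibull | 86% | 68% | 80% | 86% |
| Gamma | 96% | 95% | 79% | 89% |
| Lognormal | 99.7% | 99.5% | 81% | 95% |

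Across the four non-negative shapes the switch probability runs from 38% to 99.7%. At the cited d = 1.0, both tests exceed 99% power in every row.

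**4. Type I error with identical arms (12,000 each).** Under the either-arm switching rule, rejection is 4.5% to 5.1% at 50 per group and 4.4% to 6.0% at 10 per group. If an analyst freely takes the smaller of the two p-values, it is 5.3% to 6.8% at 50 per group.

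**5. Log scale against raw scale, 10 per group, 20,000 against 12,000.** Power of a Welch t-test on log counts against the raw t-test:
- lognormal: 71% against 61%
- gamma: 65% against 58%
- Weibull: about equal
- zero-truncated normal: 52% against 58%

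**6. Value of the baseline.** Adjustment for a covariate with correlation r removes a fraction r² of residual variance: 0.3² = 9% and 0.5² = 25%. The effective effect size is 0.57/√(1 − r²), which is 0.57/√0.91 = 0.598 or 0.57/√0.75 = 0.658. Power at 50 per group rises from about 80% to 84% or 90%. The correlations are assumed; the documents give none.

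**The case against.** The strongest defence is that a t-test with a rank fallback is familiar and does little harm here. Much of that stands, and four stronger readings that a reader might infer are not supported.

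- **That a switch is near-certain on the plan's figures.** A mean and SD do not fix a shape, and no normality test is named. About 95% or more under both checks needs gamma or lognormal counts and a formal test at 5%. A graphical check, or reliance on the central limit theorem at 50 per group, could keep the t-test.
- **That the stated power is overstated.** The t-test holds 79% to 81% under every shape tried. Wilcoxon loses about 2 points under normality and gains under skew. The raw t-test loses only relative to a better-suited analysis.
- **That the half-width of 2,273 is voided by a switch.** It describes one arm's mean, not the between-group comparison, and can be reported whichever test is used.
- **That false positives are materially inflated.** They are not under a fixed rule. The modest excess in step 4 arises only if the smaller p-value is picked, which the plan does not provide for but has no written rule to exclude.

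Two further points are fair. A Wilcoxon test does not preclude an estimate in particles, since a Hodges-Lehmann shift with its interval is standard; the gap is that none is planned. And an unadjusted comparison is valid in a randomized trial, so ignoring the baseline costs efficiency, not validity.

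What remains is that the plan neither fixes the criterion nor says what will be estimated on the rank branch.

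**Conclusion.** The concern holds as a weakness of specification and efficiency, not as an error in the sample-size figures. The primary estimand is left to the data through an unstated criterion, one branch has no planned effect estimate or interval, and collected baseline data are unused.

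The impossibility of exact normality in the device arm follows from the plan's own mean and SD. The size of the switch probability does not: it rests on the assumed shapes and on Shapiro-Wilk at 5%, which is why it is a wide range. The gain from adjustment rests on the assumed correlation. The problem does not threaten the trial's validity, but it should be corrected in the SAP because the change is cheap and settles what the trial will report.

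**What to change.** Name one primary analysis, with its estimate and 95% CI. A suitable choice is regression of each patient's log count on arm and log baseline, with heteroscedasticity-robust standard errors, reported as a geometric mean ratio. Keep Wilcoxon as a sensitivity analysis only. The text also needs:

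- **A rule for zero counts**, since their logarithm is undefined.
- **The counter that supplies the outcome and the baseline.** The plan describes two counters and designates neither as primary. The inside baseline is read with the device already on and may be affected by it. Use the outside, provider-level counter's baseline, or take the baseline before the device is placed.
- **A detectable effect restated as a ratio.** For illustration, if counts are lognormal, the log-scale SD is √ln(1 + (8,000/12,000)²) = 0.606 at the device mean and √ln(1 + (8,000/20,000)²) = 0.385 at the control mean. With d = 0.57, unadjusted, the detectable ratio is exp(−0.57 × 0.606) = 0.71 to exp(−0.57 × 0.385) = 0.80, a reduction of about 20% to 29%.

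The cost is SAP wording and standard software, plus a small change of procedure if the baseline is moved. The effect becomes a percentage reduction rather than a particle difference. The log scale can lose some power if counts are closer to a truncated normal, as step 5 of the working shows at 10 per group. If the team prefers particles, naming either existing test in advance with a matching estimate and interval would also end the data-driven choice, though without the gain from the baseline.

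### Does giving power statements for both 10 and 50 per group leave the trial's sample size open?

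*Combined protocol and SAP*

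**What the plan says.** Item 1 of Power/sample size states that "a sample size of 10 per group allows us to detect an effect size as small as 1.35 between groups", under these conditions: "using a t-test, >80% power, two sided alpha 0.05". It then turns to a similar study of containment devices, which "mentioned an effect size of 1.0 (20,000 particles vs 12,000, SD of 8,000"). The investigators expect their device to do better than any tested there, "so this is a conservative estimate of what we expect to see with our device".

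Item 2 says "Ultimately, we envision a final sample size of 50 per group to better assess both efficacy of the primary outcome", and adds more reliable secondary outcomes as a second reason. Under the same test, power and alpha it gives a detectable effect of 0.57. It also gives a precision "for the mean on our primary outcome of within +/-2,273 particles assuming the box group is 12,000 with a SD of 8,000".

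The Statistical analysis plan paragraph, just before the power section, has one primary comparison: "Particle counts will be compared between groups (device vs no device) using an independent samples t-test", with a rank-sum test as fallback. It gives no sample size and no analysis time. The document mentions no interim analysis, no stopping rule and no alpha adjustment.

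**The concern.** Two sample sizes for one test normally mean either a staged design or an unsettled one, and the document does not say which, if either, applies. Item 2 opens with a word that suggests an earlier stage, and its verb falls short of a commitment. Item 1 gives 10 per group a power statement of its own but no role as pilot, interim look or minimum.

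Item 1 also puts a size that can detect 1.35 beside the only effect the plan quantifies, 1.0. A larger effect is expected but no figure is given for it. A reader could take item 1 as support for 10 per group at the cited effect, which it is not.

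Two things would be at stake. A trial that ended at 10 per group would be underpowered for the cited effect and would estimate group means imprecisely. A trial that tested at 10 and again at 50 with no adjustment would exceed its nominal 5% error rate.

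**Working it through.** **Inputs, all from Power/sample size:** two-sided alpha 0.05; t-test; 10 and 50 per group; detectable effects 1.35 and 0.57; cited means 20,000 and 12,000 with SD 8,000, so d = (20,000 − 12,000)/8,000 = 1.0; half-width 2,273 at 50 per group.

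**Method.** Power of the two-sample t-test comes from the noncentral t distribution with 2n − 2 degrees of freedom and noncentrality d × √(n/2). The 95% half-width for one group mean is t(0.975, n − 1) × SD/√n.

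**Step 1: the plan's own figures.**

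| n per group | d | Noncentrality | Power | d at exactly 80% power |
|---|---|---|---|---|
| 10 | 1.35 | 1.35 × √5 = 3.02 | 81.4% | 1.325 |
| 50 | 0.57 | 0.57 × √25 = 2.85 | 80.6% | 0.566 |

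Half-width at 50: t(0.975, 49) × 8,000/√50 = 2,273.6, against 2,273 stated. All three figures reproduce.

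**Step 2: power at the cited effect, d = 1.0.**

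| n per group | Noncentrality | Power |
|---|---|---|
| 10 | √5 = 2.24 | 56.2% |
| 16 | √8 = 2.83 | 78.1% |
| 17 | √8.5 = 2.92 | 80.7% |
| 50 | √25 = 5.00 | 99.9% |

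The smallest size that reaches 80% at d = 1.0 is 17 per group, or 34 patients. The size called final is well above that.

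**Step 3: what 1.35 means in particles.** With 20,000 particles without a device, the device-group mean would be 20,000 − 1.35 × 8,000 = 9,200, a reduction of 10,800/20,000 = 54%. The cited effect is a reduction of 8,000/20,000 = 40%. Item 1 therefore needs a device clearly better than the cited one. That is what the investigators say they expect, though they put no number on it.

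**Step 4: precision at 10 per group.** t(0.975, 9) × 8,000/√10 = 5,723, which is 5,723/2,273.6 = 2.52 times the half-width at 50.

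**Step 5: type I error if the test were run twice (an assumption; no passage describes this).** For cumulative tests at 10 and 50 per group the correlation is √(10/50) = 0.447. Two unadjusted tests at 0.05 give an overall error of 0.0921 by the bivariate normal and about 0.092 in 200,000 simulated trials. A single test at 50 gave 0.0495 in simulation, which agrees with the nominal 5%.

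**Step 6: the two items side by side.** Item 1 says what 10 per group would allow; it does not call 10 planned or final. Item 2 calls 50 final and attaches two reasons, a detectable effect and a precision statement. The analysis paragraph has one comparison. Read together, the design is one analysis at 50 per group, and steps 1 and 2 show that this design is well powered.

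**The case for a change.** The strongest case for a change is that sample size is a core design element and should be fixed in advance beyond argument. If 50 is simply the planned size, the separate power statement for 10 does no work, and the opening word of item 2 hints at a stage that is never defined. From the text alone one cannot say for certain whether a report at 10 per group would keep to the plan or depart from it. One sentence would settle this and would need no patients beyond the 50 per group already named.

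Part of this stands. The role of 10 per group is not stated, the verb is weaker than it should be, and the document never says outright that there is one analysis. A tidier protocol would have said so.

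What does not stand is the step from loose wording to a fault in power or error rate. The 56% belongs to a trial of 10 per group, which the plan does not call final, and to an effect the investigators expect to exceed. The 9.2% belongs to a second test that no passage mentions. Item 1 is correct as labelled and makes no claim of 80% power at 1.0. The missing sample size in the analysis sentence is not telling either, because the power section follows it directly.

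**Conclusion.** The ambiguity is real but minor, and no change to the plan follows. Carried out as written, with about 50 per group and one primary test, the trial has 99.9% power at the cited effect of 1.0, 80.6% at 0.57 and a type I error of 5%. The 56% power, the ±5,723 half-width and the 9.2% error rate describe trials that the plan does not propose.

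This rests on three assumptions: that *final* means what it says, that the single comparison in the analysis section is run once, and that the cited SD of 8,000 is a fair guide. The first two are the natural reading of the text. The third is the plan's own input. Simple 1:1 randomization means the split will be close to 50 and 50 rather than exact, which does not alter the conclusion.

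If results were ever reported at 10 per group, or tested there as well as at 50, that would depart from this reading and should be judged as such.

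### Pre-op Mallampati score and thyromental distance are listed as secondary outcomes to be tested between arms, although both precede the device; they belong in a baseline table (minor).

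*Combined protocol and SAP*

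**What the plan says.** Under Secondary outcomes, the combined protocol and SAP names five variables: time to intubation, number of intubation attempts, the two parts of the "pre-op airway assessment (Mallampati score and thyromental distance"), and Cormack-Lehane grade. The Analysis plan that follows covers all of them in one sentence: "Secondary outcomes will be compared between groups (where possible) using an independent samples t-test (or chi-square test) as appropriate".

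The Intubation section fixes when the device is applied. At that stage, before preoxygenation starts, "one of the study investigators will place the device around" the patient's head. Time to intubation begins later still, as the "time from the first entry of laryngoscope into" the oropharynx.

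Three other statements bear on the point:

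- Preoperative says of randomization: "which will occur as soon as the OR schedule is available for viewing".
- The same section adds: "The study investigator will obtain consent the day of surgery".
- Exclusion criteria lists, as one item in a series: "Patients predicted to be difficult mask ventilation or intubation (as determined by anesthesiologist), or".

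The document describes no baseline table and no covariate adjustment. It does not say when the airway is assessed or by whom.

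**The concern.** An outcome is something the intervention could change. By their own label, Mallampati score and thyromental distance are recorded pre-operatively, and the device is placed only at the intubation stage. A between-arm test on either one therefore answers no question about the device. The phrase about comparing where possible does not exempt them, because a Mallampati class suits a chi-square test and a distance suits a t-test.

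Two things are at stake. First, a chance difference in one of these measures could be reported as a secondary finding. Second, the data are not used where they could help: to describe the arms, and perhaps to sharpen the comparison of time to intubation, which shows whether the device hampers the procedure.

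**Working it through.** **Inputs from the document (Power/sample size).** 10 per group and then 50 per group; detectable effects 1.35 and 0.57 SD; power above 80%; two-sided alpha 0.05; t-test.

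**Assumption.** R², the share of variance in time to intubation explained by the two airway measures. The document gives no value, so a range is shown.

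**1. The plan's own figures.** By the noncentral t with 2n−2 degrees of freedom, 1.35 SD at n = 10 has 81.4% power and 0.57 SD at n = 50 has 80.6%. The exact 80% detectable differences are 1.325 and 0.566 SD. The stated figures reproduce, and none of them depends on the airway measures.

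**2. Two tests of pre-device variables.** With no true difference and independence, the chance of at least one p<0.05 is 1 − 0.95² = 9.75%. Whatever the dependence, it cannot exceed 0.05 + 0.05 = 10%. Positive correlation lowers it, to about 9.1% at an assumed correlation of 0.5.

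**3. Adjusting time to intubation.** With N = 2n and k covariate terms, the variance of the adjusted difference, in SD² units, is

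(2/n) × (1 − R²) × (N − 3)/(N − 3 − k), on N − 2 − k degrees of freedom.

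At n = 50 and k = 2 (Mallampati as one linear term, plus thyromental distance), the penalty is 97/95 = 1.021. At R² = 4% the detectable difference is multiplied by about √(0.96 × 1.021) = 0.990, and 0.566 × 0.990 = 0.560. The noncentral t results are:

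| R² (assumed) | Detectable difference, n = 50 | Power at 0.566 SD |
|---|---|---|
| Unadjusted | 0.566 | 80.0% |
| 0 | 0.572 | 79.2% |
| 4% | 0.560 | 80.8% |
| 10% | 0.543 | 83.2% |
| 25% | 0.495 | 89.3% |

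Break-even R² is 2.1%. The worst-case cost is 0.572 − 0.566 = 0.006 SD.

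**4. Coding of Mallampati.** As four classes (k = 4), the penalty is 97/93 = 1.043. Break-even rises to 4.2% and the worst case to 0.578 SD, a loss of 0.012. At R² = 4% the detectable difference is 0.5665 SD against 0.5659 unadjusted, so the gain disappears.

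**5. Ten per group.** With k = 2 the penalty is 17/15 = 1.133 and break-even R² is 13.1%. At R² = 4% the detectable difference worsens from 1.325 to 1.392 SD, and power at 1.325 SD falls from 80% to 76.0%.

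**6. Validity.** In 10,000 simulated trials per setting, with k = 2 and R² of 10% or 20%, type I error was about 5% with and without adjustment at both sizes. Restricting adjustment to 50 per group is a choice about precision; validity does not require it.

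**The case against.** **Adjustment is a preference.** Leaving a secondary outcome unadjusted is legitimate, and R² is wholly assumed. Predicted-difficult airways are excluded, which narrows both covariates, so the low end is the likelier case. There the gain is 0.8 percentage points of power, and it vanishes under four-class coding. This stands, and it is why adjustment can only be a supporting analysis with the coding fixed in advance.

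**The measures may not precede knowledge of allocation.** A reader might infer that pre-op means before randomization. The document shows only that the measures precede the device. Randomization happens when the OR schedule appears, and providers are informed then. Mallampati grading is subjective, and adjustment would not fully repair scoring done with the allocation known. This also stands, and it makes adjustment conditional.

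**A comparison between arms might reveal selective exclusion.** A reader might infer that a baseline table would settle whether exclusions or refusals after randomization were selective. It would not. Patients lost after allocation are not in a table of analysed patients, and the document does not provide for their airway data, so the evidence is indirect.

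**The harm is small.** A reader would have to attribute a variable labelled pre-op to the device, and 9.75% assumes independence although both items assess the same airway. That is fair, and the figure is best read as near a ceiling. It does not make the tests informative about the device.

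**They may have been meant as descriptors.** If so, moving them states that intent and removes tests that the current wording calls for.

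**Conclusion.** The classification is wrong: two of the five listed secondary variables cannot respond to the device, yet the plan calls for testing them between arms. If there is no true difference, the chance of at least one uninformative p<0.05 is up to about 10%.

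It would be tempting to conclude that the comparison of time to intubation is invalid without these covariates. The document does not support that. Under randomization the unadjusted comparison is valid, and adjustment offers only a modest gain in precision that depends on the assumed R². No alpha is allocated to secondary outcomes, and no conclusion on the primary outcome turns on this point. The severity is minor.

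**What to change.** 1. Move Mallampati score and thyromental distance from Secondary outcomes to a baseline table by arm, without p-values.
2. State when the airway is assessed and by whom.
3. Provided both measures are recorded before the assessor knows the allocation, pre-specify one supporting analysis at 50 per group only: time to intubation adjusted for Mallampati class (one linear term) and thyromental distance. Do not let a baseline p-value trigger it.
4. Keep the unadjusted comparison as the main result. Report both as mean differences with 95% CIs on the same scale. If a log scale is wanted for skewness, fix it in advance and use it for both.

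Item 1 changes SAP wording only; both measures are already planned and no patients are added. Items 2 and 3 may also require the grading to be done before the allocation is disclosed. If that cannot be arranged, omit item 3; item 1 stands without it.

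### Secondary outcomes are given only an unassigned t-test or chi-square test; an uncollapsed chi-square on Cormack-Lehane grade or number of attempts would lose power that a rank test keeps (minor)

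*Combined protocol and SAP*

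**What the plan says.** In the combined protocol and SAP, the analysis plan under Secondary outcomes is one sentence: "Secondary outcomes will be compared between groups (where possible) using an independent samples t-test (or chi-square test) as appropriate". The outcomes it covers include "total number of intubation attempts", "laryngoscopy grade view (Cormack-Lehane) obtained during intubation" and time to intubation. No outcome is matched to a test, and no rank, exact or ordinal method is named.

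The primary outcome is treated differently. Under Statistical Methods, particle counts are compared "using an independent samples t-test (or Wilcoxon Rank Sum Test if distributional assumptions are violated").

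Two other parts of the document matter. The exclusion criteria remove "Patients predicted to be difficult mask ventilation or intubation". Power/sample size gives two group sizes: "a sample size of 10 per group allows us to detect an effect size as small as 1.35 between groups", and later "we envision a final sample size of 50 per group". It gives no power figure for any secondary outcome and no expected frequencies for grade or attempts.

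**The concern.** The latitude in the secondary sentence is a choice between two named tests. For a graded outcome, most readers would take the chi-square test as the one meant. That has two drawbacks here. It treats grades I to IV as unordered labels, so it spreads its sensitivity over patterns that nobody expects. Its reference distribution also relies on adequate expected counts, which are unlikely once predicted difficult airways are excluded.

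At stake is how much these comparisons can show about intubation with the device in place. The sample-size section gives more reliable secondary outcomes as one reason for going to 50 per group. An inefficient test gives part of that benefit back.

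**Working it through.** **1. The plan's own figures.** These concern the primary outcome only, but they confirm the group sizes used below. A two-sample t-test, two-sided 0.05, has 81.4% power at 10 per group and effect size 1.35, and 80.6% at 50 per group and 0.57. The half-width is t(0.975, 49) × 8,000/√50 = 2.0096 × 1,131.4 = 2,273.6, against the stated 2,273. All three reproduce.

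**2. Sparsity by arithmetic.** With equal groups of n, the expected count in a cell is n × the pooled share of its category.
- 10 per group: expected counts in a group sum to 10. Over three observed categories they average 10/3 = 3.3, and over four 10/4 = 2.5. At least one is therefore below 5 whenever three or more categories occur.
- 50 per group: 50 × share < 5 whenever the share is below 10%. Whether that happens depends on frequencies the documents do not give. The airway exclusion makes it likely but does not establish it.

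**3. Power by simulation.** The inputs are assumptions: control distributions for four grades and three attempt categories, shifted by a common odds ratio (OR) at every cut. Example: grades 60/30/8/2% with OR 2.5. The odds of grade I are 0.60/0.40 = 1.5; 1.5/2.5 = 0.6; 0.6/1.6 = 37.5%. The whole shifted distribution is 37.5/40.8/16.9/4.9%. The tests are Pearson chi-square on all observed categories, tie-corrected Wilcoxon, and a t-test on the category scores, each two-sided at 0.05. There were 100,000 trials per setting (20,000 where marked *).

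Grade, 50 per group, OR 2.5:

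| Control grades I-IV (%) | Chi-square | Wilcoxon | t-test |
|---|---|---|---|
| 50/30/15/5 | 51.9% | 69.4% | 68.4% |
| 60/30/8/2 | 48.4% | 66.7% | 64.2% |
| 65/25/8/2* | 46.8% | 65.1% | 62.3% |
| 75/20/4/1 | 41.1% | 59.0% | 55.3% |

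Chi-square loses 17.5 to 18.3 points against Wilcoxon; the t-test loses 1.0 to 3.7. Allowing for simulation error between runs, the ranges are about 41-53% and 59-70%.

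Attempts, 50 per group:

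| Control 1/2/3+ (%) | OR | Chi-square | Wilcoxon | t-test |
|---|---|---|---|---|
| 88/10/2* | 3 | 44.0% | 56.4% | 53.8% |
| 90/8/2 | 2.5 | 26.3% | 36.6% | 34.5% |
| 90/8/2 | 3.5 | 52.3% | 64.7% | 61.8% |
| 95/4/1 | 2.5 | 14.4% | 21.7% | 19.9% |
| 95/4/1 | 3.5 | 30.2% | 42.1% | 39.3% |

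At OR 3, across 88/10/2% to 95/4/1%, this is about 20-45% for chi-square and 30-58% for Wilcoxon.

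At 10 per group every test is weak. For grade at OR 2.5, chi-square has 8.4-10.2% power and Wilcoxon 15.1-18.5%.

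**4. Type I error.** With no effect and 50 per group, chi-square rejects in 2.6-4.5% of trials and Wilcoxon in 4.6-5.1%, over grades from 50/30/15/5% to 75/20/4/1% and attempts from 85/12/3% to 95/4/1%. The usual rule for chi-square (at most 20% of expected counts below 5, none below 1) fails in 96-99% of these null tables.

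**The case against.** The strongest reply is that the plan also permits a t-test. On grade or attempts at 50 per group, the t-test comes within about 4 points of Wilcoxon and close to nominal size. This stands: the loss follows only if chi-square is chosen, and it would be wrong to say that neither permitted test serves. The plan does not make that choice, however, and a t-test on grade yields a mean difference with no clear meaning.

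Second, the loss needs the categories left uncollapsed. Under 65/25/8/2% and OR 2.5, a chi-square test of grade I against II-IV has 63.6% power. For first-attempt success under 88/10/2% and OR 3 it has 57.7%. This also stands, but no collapsing is planned.

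Third, the frequencies and odds ratios are assumed. That is so, which is why a range is shown. Only the result at 10 per group with three or more categories is forced by arithmetic.

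A reader might go further in three ways that the documents do not support.
- **Inflated false positives from sparse cells.** Every departure found for the uncollapsed chi-square was conservative. Rejecting whenever either permitted test is significant would raise the error (7.7% for grade at 50 per group in one simulation), but nothing says the investigators would do that.
- **A failed safety check.** The plan does not label these outcomes as harm endpoints and powers none of them. Wilcoxon would not make them an adequate check either, at 59-70% power for grade and OR 2.5.
- **Intubation time must be analysed on the log scale.** The documents give no figure on its distribution.

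**Conclusion.** The point holds as a minor one. The plan leaves the test for each secondary outcome open. The natural choice for an ordered grade, an uncollapsed chi-square, costs about 17-18 points of power against a rank test at OR 2.5 and 50 per group. For attempts at OR 3 the cost is about 10-13 points.

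These sizes rest on assumed distributions, a common odds ratio across cuts, equal groups and the large-sample tie-corrected Wilcoxon test. The direction was the same in every setting tried at 50 per group. The error is towards missing a difference. The primary analysis and its conclusion are untouched.

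**What to change.** Under Secondary outcomes, Analysis plan, state that:
- Cormack-Lehane grade and number of attempts are compared by the Wilcoxon rank-sum test, tie-corrected, with an exact or permutation p-value when counts are small;
- first-attempt success is reported descriptively as a risk difference with a 95% CI and no second test;
- time to intubation is compared by t-test, with the primary outcome's Wilcoxon fallback if distributional assumptions are violated.

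A Fisher's exact test on first-attempt success is best left out. For 88% against 71% at 50 per group it has 47.7% power and 2.1% size, little better than the uncollapsed chi-square, and it would put two tests on one outcome without saying which governs.

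The cost is a wording change, with the same data and standard software. The drawback is that a rank test gives no directly interpretable effect size; the risk difference supplies one for attempts, but grade would still lack one.
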